Qualified personnel who are familiar with procedures that minimize undue exposure to them and to the environment should undertake the preparation, handling, and safe disposal of chemotherapeutic agents in an appropriate environment.

5.4 **Dose Modifications and Dosing Delays**

Patients who experience a dose limiting toxicity (as defined in section 6.2.1) will stop the study drugs and come off of the trial. The dose cohort level will be de-escalated to 75mg PO daily if dose limiting toxicity occurs in the initial 100mg dose cohort.

Patients who complete the first cycle of maintenance but require treatment to be held up to 4 weeks (after the end of the cycle) to achieve count recovery (as defined below), will have palbociclib resumed with a level -1 dose reduction.

For this study, count recovery is defined as $\geq 10\%$ cellularity in the bone marrow, neutrophils $\geq 0.75 \times 10^{9}$ /L, and a platelet count $\geq 75 \times 10^{9}$ /L.

	Dose*							
Dose Level	Palbociclib (mg)	Dexamethasone (mg)						
Level -1	75	20						
Level 1	100	20						
Level 2	125	20						
Level 3	150	20						

For patients who remain on maintenance after the first cycle, palbociclib dose modifications will be made as follows:

Hematologic toxicity (except lymphopenia unless associated with clinical events [eg opportunistic infection]), according to Common Toxicity Criteria for Adverse Events Version 4.03:

Neutropenia:

Grade 1 or 2: No dosage adjustment required.

Grade 3:

- Day 1 of cycle: Withhold palbociclib therapy and repeat CBC with differential within 1 week. When improved to ≤ grade 2, initiate the next cycle at the same dose. If recovery from grade 3 neutropenia is prolonged (>2 weeks), or for recurrent grade 3 neutropenia on day 1 of subsequent cycles, decrease to next lower dose.
- Grade 3 (ANC 500/mm³ to <1,000/mm³) plus fever ≥38.5°C and/or infection at any time: Withhold palbociclib treatment until resolved to ≤ grade 2. Resume at the same dose.Grade 4 at any time: Withhold palbociclib treatment until resolved to ≤ grade 2. After resolution, resume at next lower dose.

Anemia:

Grade 1, 2, or 3: No dosage adjustment required

Grade 4: Withhold palbociclib treatment until resolved to ≤ grade 2. After resolution, resume at next lower dose.

Thrombocytopenia:

Grade 1 or 2: No dosage adjustment required.

Grade 3:

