	 Grade 3 indirect hyperbilirubinemia that resolves to < grade 2 within 72 hours 								
Renal	Any ≥ Grade 3 toxicity								
Non-	≥ Grade 3, including electrolyte abnormalities, except as noted elsewhere in								
Hematologic	the table								
Exceptions to	Grade 3 alopecia								
DLI criteria	Grade 3 fatigue of < 5 days' duration								
	Grade 3 electrolyte abnormalities that last <72 hours								
	 Infection (including neutropenic fever), unless the investigator 								
	determines that the infection or neutropenic fever resulted from the degree or duration of myelosuppression in the absence of persistent								
	ieureillia								

* CTCAE version 5.0 should be used for grading.

** Optimal therapy for vomiting and diarrhea should be based on institutional guidelines with consideration of the prohibited medications listed in these protocol guidelines.

The DLT evaluation period is defined as 35 days (one week lead-in plus Cycle 1). In order to be considered evaluable, the patient needs to take 80% of the doses in the one week lead-in and Cycle 1 (1 cycle=28 days). The 80% completion can be non-consecutive days of dosing with study drug within the one week lead-in and Cycle 1. Any DLT will be followed until resolution.

If one DLT is recorded, then three additional patients will be enrolled into the present cohort. If no further DLTs occur (1 out of 6 DLTs) then the next patient will be enrolled in the next higher cohort. If 2 out of 6 patients have an observed DLT in any given cohort, 3 additional patients will be treated at one dose level lower, and if no additional DLTs are observed, this will be the maximum tolerated dose. If no DLTs are observed in all three cohorts then the expansion phase dose will be cohort 3 for the expansion phase. Toxicities will be graded according to the National Cancer Institute, Common Toxicity Criteria for Adverse Events version 4.0 (NCI CTCAE v5.0). If multiple toxicities are seen, the presence of DLT will be based on the most severe toxicity experience.

Once three patients have enrolled onto the dose cohort and the DLT evaluation period or the third patient has passed, a meeting will be held with the PI and the TJU Medical Monitor to review the safety information. If it is determined safe to open the next dose cohort, a formal letter from the Medical Monitor will be issued. Please see Appendix D for more information.

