** Optimal therapy for vomiting and diarrhea should be based on institutional guidelines with consideration of the prohibited medications listed in these protocol guidelines.

The design is constructed to reduce the chance of escalating the dose when the probability of DLT is high, and increase the chance of escalating the dose when the probability of DLT is low. The maximum tolerated dose (MTD) is defined as the highest dose level where a DLT occurs in at most one out of six patients treated. The escalation scheme is as follows:

(1) If none of the initial three patients in a cohort experiences a DLT, then a new cohort of three patients will be treated at the next higher dose level.

(2) If one of the three patients in a cohort experiences a DLT, then up to three additional patients will be treated at the same dose. Escalation will continue if only one of six patients experiences DLT.

(3) If two or more patients in a cohort experience DLT, then the MTD will have been exceeded, and no further dose escalation will occur. The previous dose level will be considered the MTD.

(4) If only three patients were treated at a dose level under consideration as the MTD, then up to three additional patients will be accrued. If no more than one of the six patients at that dose level experience a DLT, then that dose level will be confirmed as the MTD. If two or more patients in that cohort experience DLT, then the previous dose level will be studied in the same fashion.

The MTD is defined as the highest dose studied for which the observed incidence of DLT is less than 33%. Frequencies of toxicities will be tabulated according to the NCI Common Toxicity Criteria. Patients will be continued to be followed for one year for evidence of late toxicity.

Table 1.1 below gives the probabilities of dose escalation based on true DLT risk in the 3+3 design.

True DLT rate										
		10%	20%	30%	40%	50%	60%	70%	80%	90%
Probability c escalation	of	0.91	0.71	0.49	0.31	0.17	0.08	0.03	0.01	0.001

All patients treated with at least one dose will be included in the safety analysis.

Response criteria for the study are defined as follows:

Response Criteria Complete Remission (CR) No lymphoblasts in the bone marrow Absolute neutrophil count ≥0.75 x10⁹/L Platelet count ≥75 x 10⁹ /L

Complete Remission with Incomplete Hematologic Recovery (CRi)

<5% lymphoblasts in the bone marrow

Partial Remission (PR)

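### After a de-escalation, Section 6.2.1 names the MTD on no DLT in three additional patients, while Section 11.2 requires at most one DLT in six

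*Combined protocol and SAP*

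**What the plan says.** Section 2.2.1 makes DLT and MTD the primary endpoint. Three sections govern what happens after toxicity.

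- **Section 6.2.1.** After a first DLT: "If one DLT is recorded, then three additional patients will be enrolled into the present cohort". De-escalation follows "If 2 out of 6 patients have an observed DLT in any given cohort"; then "3 additional patients will be treated at one dose level lower, and if no additional DLTs are observed, this will be the maximum tolerated dose". Two or more DLTs among the first three patients are not mentioned.
- **Section 11.2.** After one DLT in three (rule 2), "then up to three additional patients will be treated at the same dose". Rule 3: "If two or more patients in a cohort experience DLT, then the MTD will have been exceeded", and "The previous dose level will be considered the MTD". Rule 4 adds up to three patients to a candidate level that has only three, and confirms it if no more than one of the six has a DLT. The MTD is defined as the "highest dose level where a DLT occurs in at most one out of six patients treated", and a second time as the highest dose studied with an observed DLT incidence below 33%. The doses listed are 100, 125 and 150 mg.
- **Section 5.4.** "The dose cohort level will be de-escalated to 75mg PO daily if dose limiting toxicity occurs in the initial 100mg dose cohort". No count is given.

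The dose tables in Sections 5.4 and 6.2.1 include level -1 at 75 mg, and Section 11.3 describes patients being treated there. Section 3 refers the reader to Section 11 for the design. Section 3.1 sets a maximum of 18 patients; Section 11.3 states both 24 and 18.

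**The concern.** The decision rule determines the primary result, so the same outcomes should lead to the same MTD whichever section the team follows. Here they need not. Three patients without a DLT at the lower level settle the matter under Section 6.2.1. Under rule 4 a level with only three patients is taken to six. A single DLT among the additional patients blocks the MTD under Section 6.2.1 but is allowed under rule 4 if it is the only one in six.

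The sample behind the MTD also differs. At a level that already has three patients, three more make six under either section. At 75 mg nobody has been treated before, so Section 6.2.1 would name the MTD on three patients.

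**Working it through.** **Inputs.** The rules are those of Sections 5.4, 6.2.1 and 11.2. The protocol assumes no DLT rate, so true rates p of 10 to 40%, part of the range in Table 1.1, are used as assumptions. Write q = 1 - p.

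**Check on the plan's own figures.** Under rules 1 and 2, P(escalate) = q³ + 3pq² × q³. At p = 0.1 this is 0.729 + 0.243 × 0.729 = 0.906, against 0.91 in Table 1.1. All nine entries reproduce. The tabulated design therefore expands to six after one DLT.

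**A lower level with 0 of 3 already.** Rule 4 accepts zero or one DLT in the next three patients; Section 6.2.1 accepts only zero. They disagree when exactly one occurs (1 of 6 in total), with probability 3pq².

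**Level -1, no earlier patients.** Section 6.2.1 accepts with probability q³. At most one in six has probability q⁶ + 6pq⁵. On the same six outcomes they disagree in two ways:
- 0 of the first 3, then two or more of the next 3: q³(3p²q + p³). Section 6.2.1 accepts; the six-patient test rejects.
- 1 of the first 3, then 0 of the next 3: 3pq² × q³ = 3pq⁵. Section 6.2.1 rejects; the six-patient test accepts.

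**Reaching 75 mg directly from 100 mg by the literal Section 6.2.1 trigger.** This needs one DLT in the first three and one in the next three: (3pq²)².

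| True DLT rate | 10% | 20% | 30% | 40% |
|---|---|---|---|---|
| Level with 0/3 already: disagreement, 3pq² | 0.243 | 0.384 | 0.441 | 0.432 |
| 75 mg accepted, 0 of 3 | 0.729 | 0.512 | 0.343 | 0.216 |
| 75 mg accepted, at most 1 of 6 | 0.886 | 0.655 | 0.420 | 0.233 |
| 75 mg: 0/3 passes, six-patient test fails | 0.020 | 0.053 | 0.074 | 0.076 |
| 75 mg: 0/3 missed, 1/6 passes | 0.177 | 0.197 | 0.151 | 0.093 |
| 75 mg: total disagreement | 0.198 | 0.250 | 0.225 | 0.169 |
| Literal 6.2.1 trigger at 100 mg | 0.059 | 0.147 | 0.194 | 0.187 |
| Trigger × disagreement, same rate at both doses | 0.012 | 0.037 | 0.044 | 0.032 |

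**Which test is stricter.** The two acceptance probabilities are equal when 1 = q³ + 6(1 - q)q², so q = (1 + √21)/10 = 0.558 and p = 0.442. Below a true rate of 44%, 0 of 3 is the harder test to pass.

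**Precision.** Exact two-sided 95% intervals for the DLT rate: 0/3, 0 to 71%; 0/6, 0 to 46%; 1/6, 0.4 to 64%.

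**Trigger for leaving 100 mg.** Section 5.4 read literally (any DLT in the first three) gives 1 - q³ = 0.271, 0.488, 0.657, 0.784. Rules 2 and 3 (two or more DLTs) give 1 - (q³ + 3pq⁵) = 0.094, 0.291, 0.506, 0.691.

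**The case against.** The best defence is that the intended design is clear and the rest is loose drafting. Much of that stands.

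- A reader might infer from Section 5.4 that one DLT at 100 mg sends the cohort to 75 mg. Its sentence is more naturally shorthand: Section 6.2.1, rule 2 and Table 1.1 all expand to six after one DLT, and Section 11.3 speaks of two or more in the first three. It still needs a count, because Section 6.2.1 refers readers to Section 5.4 for dose modifications.
- A reader might infer that Section 11.2 has no rule for 100 mg failing in its own first cohort, or that it would name an untreated 75 mg the MTD. Rule 3 applies to any cohort, so it covers that failure, and both definitions concern doses actually treated or studied. What remains is that Section 11.2 does not list 75 mg and rule 4 speaks of a level with only three patients, not none.
- 0 of 3 does satisfy the second definition in Section 11.2 (below 33%). But rule 4 would still accrue to six, so this does not reconcile the sections.
- A reader might multiply the disagreement at 75 mg by the chance that 100 mg fails in any way (0.094, 0.291, 0.506, 0.691), giving 0.02, 0.07, 0.11 and 0.12. That overstates the conflict: where two or more of the first three have DLTs, Section 6.2.1 is silent and only Section 11.2 speaks.
- The gain in precision is modest: an upper limit of 71% for 0/3, against 64% for the 1/6 that Section 11.2 accepts.

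The difference between no DLT in three additional patients and at most one in six survives all of this. The Medical Monitor review in Section 6.2.1 does not say which test governs.

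**Conclusion.** The conflict is real and lies in the operative text. After de-escalation, Sections 6.2.1 and 11.2 can give different MTD decisions on the same data, at any lower level. Given that 75 mg is reached, they disagree with probability of about 0.17 to 0.25 at true DLT rates of 10 to 40%. With the literal Section 6.2.1 trigger and the same rate at both doses, the figure is about 0.01 to 0.04. These values are illustrative, because the protocol assumes no DLT rate.

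A reader might infer that Section 6.2.1 lets toxic doses through. The arithmetic does not support that below a true rate of 44%, where its test is the stricter one. The harm is ambiguity in a primary endpoint and, at 75 mg, an MTD resting on three patients. The Section 5.4 wording, the silence of Section 6.2.1 on two or more DLTs in the first three, and the missing level -1 in Section 11.2 are secondary. The text should be corrected; Table 1.1 needs no change.

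**What to change.** - **Sections 5.4 and 6.2.1:** de-escalate on two or more DLTs among three to six patients at a level.
- **Section 6.2.1:** confirm any lower level as the MTD only with at most one DLT in six evaluable patients.
- **Section 11.2:** list level -1 (75 mg); apply rule 4 to any candidate level with fewer than six evaluable patients, including none; declare no MTD if level -1 has two or more DLTs.
- **Sections 3.1 and 11.3:** state one maximum enrolment that fits this rule.

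The cost is wording plus a decision on the cap. The direct path from 100 to 75 mg needs at most 6 + 6 = 12 evaluable patients, within 18. If every one of the four levels can reach six, the maximum is 4 × 6 = 24 evaluable patients, which exceeds the 18 in Section 3.1. Replacements for non-evaluable patients under Section 11.3.1 come on top.

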11.2 Analysis Plans

This aim will consist of a Phase I trial of palbociclib to determine the maximum tolerated dose (MTD) of palbociclib when given in combination with dexamethasone. A standard 3+3 dose escalation design will be employed: three dose levels of palbociclib will be explored (100mg, 125mg, 150mg). Patients will be treated in cohorts of size three to six and the dosage will be escalated if the clinical toxicity is acceptable.

Patients who experience a DLT during the evaluation period as defined in section 6.2.1 will stop the study drugs and come off of the trial.

Patients who complete the first cycle of maintenance but require treatment to be held up to 4 weeks to achieve count recovery, will have palbociclib resumed with a level -1 dose reduction. A dose-limiting toxicity (DLT) is defined in the table below:

Toxicity	DLT Criteria*								
Hematology	 Marrow aplasia (defined as <10% cellularity with <10% blasts for ≥ 6 weeks not attributable to disease) 								
	• Grade 4 neutropenia persisting ≥6 weeks from the start of a cycle that								
	is not attributable to the underlying disease								
Cardiac	Any ≥ Grade 3 toxicity								
Gastro-intestinal	Any ≥ Grade 3 toxicity except:								
	 Grade 3 nausea, vomiting**, or diarrhea** not requiring total parenteral nutrition (TPN) or tube-feeding 								
Hepato-biliary	An increase in AST or ALT >3 x ULN and concurrent increase in total								
	bilirubin >2 x ULN (Hy's Law)								
	Any \geq Grade 3 toxicity except:								
	Any Grade 3 or 4 liver abnormalities (AST, ALT, or alkaline								
	phosphatase) that resolve to < grade 2 within 72 hours								
	 Grade 3 hyperbilirubinemia that resolves to < grade 2 within 72 hours One de 2 in dimensional that resolves to < grade 2 within 72 hours 								
	 Grade 3 indirect hyperbilirubinemia that resolves to < grade 2 within 72 hours 								
	nours								
Renal	Any ≥ Grade 3 toxicity								
Non-	≥ Grade 3, except as noted elsewhere in the table								
Hematologic									
Exceptions to	Grade 3 alopecia								
DLT criteria	 Grade 3 fatigue of < 5 days' duration 								
	 Grade 3 electrolyte abnormalities that last <72 hours 								
	 Infection, unless the investigator determines that the infection resulted 								
	from the degree or duration of myelosuppression in the absence of persistent leukemia								

* CTCAE version 5.0 should be used for grading.

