11.3 Sample Size Considerations

This traditional 3+3 dose escalation study will include a minimum of 4 and a maximum of 24 participants. The minimum sample size of 4 would be achieved if \geq 2 patients out of the first 3 patients have a DLT at dose levels 1 and -1. The maximum sample size of 18 would be achieved if 6 patients are enrolled at dose levels -1 through 3 (100 mg, 125mg, 150mg, 175mg). The anticipated sample size is 12-18.

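### Sections 6.2.1 and 11.2 use the same escalation step but different rules for confirming the MTD, which is the primary endpoint

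*Combined protocol and SAP*

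**What the plan says.** Section 2.2.1 makes DLT and MTD the primary endpoint. Both 6.2.1 and 11.2 escalate after 0/3 DLTs, expand to six after 1/3, and escalate at 1/6. They part after that.

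- **Fallback, 6.2.1.** After 2/6 DLTs, three more patients are treated one level lower, with no condition on how many that level already has; "if no additional DLTs are observed, this will be the maximum tolerated dose".
- **Fallback, 11.2 rule (4).** "If only three patients were treated at a dose level under consideration as the MTD, then up to three additional patients will be accrued". Then: "If no more than one of the six patients at that dose level experience a DLT, then that dose level will be confirmed". This agrees with the definition of the MTD given just before the rules, "the highest dose level where a DLT occurs in at most one out of six patients treated". The section also says "Patients will be treated in cohorts of size three to six".
- **Top dose, 6.2.1.** "If no DLTs are observed in all three cohorts then the expansion phase dose will be cohort 3 for the expansion phase". Rule (4) contains no exception for the top dose.
- **Move to 75 mg.** Section 5.4 says "The dose cohort level will be de-escalated to 75mg PO daily if dose limiting toxicity occurs in the initial 100mg dose cohort", with no DLT count. Section 11.3 bases its minimum sample size on at least "2 patients out of the first 3 patients have a DLT at dose levels 1 and -1".

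Section 3 refers the reader to Section 11 for the 3+3 design. Nothing in the text says which section prevails if they disagree.

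**The concern.** Three situations that arise in the ordinary course of a 3+3 trial are handled differently.

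- **1a.** The lower level stood at 0/3 and then shows one DLT in three more patients. Under 11.2 it is the MTD (1/6). Section 6.2.1 does not name it and gives no next step.
- **1b.** The lower level already stands at 1/6. Under 11.2 it is the MTD with no further patients. Section 6.2.1 adds three, making nine, which is outside the three to six per cohort in 11.2.
- **2.** There are no DLTs at 100, 125 or 150 mg. Section 6.2.1 takes 150 mg forward on three patients; 11.2 adds up to three first. Section 1.2 reports a single-agent MTD of 125 mg in solid tumours, so three patients are thin support for 150 mg. The expansion phase is not defined in the available text, and 11.3 counts no patients for it.

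At stake are the dose reported as the primary result and the dosing of three patients in either direction. Section 6.2.1 is the operational section. Unless the conflict is removed beforehand, the choice between the sections would be made with the DLT data in view.

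**Working it through.** **Inputs.** The rules are those of 6.2.1 and 11.2. The protocol assumes no DLT rates, so the rates below are assumptions. Write p for the true DLT rate and B(k) for the binomial probability of k DLTs in three patients.

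**The plan's own figure.** P(escalate) = B(0) + B(1)·B(0) = (1−p)³ + 3p(1−p)⁵. At p = 0.1 to 0.9 this gives 0.906, 0.709, 0.494, 0.309, 0.172, 0.082, 0.032, 0.009, 0.001. All nine entries of Table 1.1 reproduce. The table covers escalation only, so it cannot decide between the two confirmation rules.

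**Given that each situation has arisen.**

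| Situation | Formula | Result |
|---|---|---|
| 1a: 0/3, then exactly one DLT in three | 3p(1−p)² | 24%, 38%, 44% at p = 10%, 20%, 30% |
| 1b: 1/6, then at least one DLT in the three that only 6.2.1 adds | 1−(1−p)³ | 27%, 49%, 66% at p = 10%, 20%, 30% |
| 2: 0/3 at 150 mg, then rejected by rule (4) | 3p²(1−p) + p³ | 22%, 35%, 50% at p = 30%, 40%, 50% |

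Equivalently, a level first cleared at 0/3 is confirmed with probability (1−p)³ under 6.2.1 and (1−p)³ + 3p(1−p)² under 11.2. These are 51% against 90% at p = 20%, and 34% against 78% at p = 30%.

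**Over the whole trial,** by exact enumeration from 100 mg:

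- S1a = sum over the exceeded level (125 or 150 mg) of P(reach the level below) × B(0) there × P(trigger at the exceeded level) × B(1) at the level below.
- S1b = the same sum with B(1)·B(0) for the level below, so S1b = S1a.
- S2 = product of B(0) over the three levels.
- P(trigger) = B(1)² for exactly 2/6, or 1 − P(escalate) for two or more DLTs.

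Example, rates 10/20/30%, exactly 2/6:

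- 125 mg exceeded: 1 × 0.729 × 0.384² × 0.243 = 0.026.
- 150 mg exceeded: 0.906 × 0.512 × 0.441² × 0.384 = 0.035.
- S1a = S1b = 0.061, and S2 = 0.729 × 0.512 × 0.343 = 0.128.
- Sum = 0.250.

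The accepted level differs in all of S1a, in S1b when at least one of the three extra patients has a DLT, and in S2 when at least two of rule (4)'s extra three do. Differing here means that 11.2 names a level which 6.2.1 does not, or that 6.2.1 carries forward 150 mg when rule (4) rejects it.

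| Assumed rates at 100/125/150 mg | Trigger | S1a = S1b | S2 | Any of the three | Accepted level differs |
|---|---|---|---|---|---|
| 10/15/20% | exactly 2/6 | 0.045 | 0.229 | 32% | 8.5% |
| 10/20/30% | exactly 2/6 | 0.061 | 0.128 | 25% | 11.2% |
| 20/30/40% | exactly 2/6 | 0.058 | 0.038 | 15% | 10.3% |
| 10/15/20% | two or more | 0.086 | 0.229 | 40% | 14% |
| 10/20/30% | two or more | 0.142 | 0.128 | 41% | 23% |
| 20/30/40% | two or more | 0.173 | 0.038 | 39% | 28% |

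Fallback from 100 mg to an untested 75 mg is not counted. A simulation of 400,000 trials at 10/20/30% with the two-or-more trigger gave 0.142, 0.142 and 0.128 for the three situations, in agreement.

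**The case against.** The best defence is that 6.2.1 is incomplete and does not contradict 11.2. Its sentence gives a sufficient condition for the MTD; it does not say the condition is necessary. Section 3 points to Section 11, so rule (4) would supply the missing step in 1a. The nine patients in 1b come from a literal reading; completing the level to six would fit the 3+3 framework and the cohort limit in 11.2. One further DLT there would give 2/9 = 22%, which still meets the second MTD definition in 11.2 (observed incidence below 33%). In situation 2 the sentence sets an expansion dose and does not declare an MTD, and Appendix D, whose title mentions expansion, is not available. Where 6.2.1 is the stricter rule, it errs on the side of caution.

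Part of this stands. In 1a and 1b, 6.2.1 often names no dose at all. Counting only trials in which both sections point to a dose and disagree leaves S2 × P(at least two of three): 0.229 × 0.104 = 2.4%, 0.128 × 0.216 = 2.8% and 0.038 × 0.352 = 1.3%. The two-or-more rows combine the 11.2 trigger with the 6.2.1 confirmation rule. Because 6.2.1 is silent on two or three DLTs in the first three patients, those rows are upper bounds.

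The claim itself survives. The reference in Section 3 is a cross-reference and sets no precedence. If 6.2.1 is read as assuming 0/3 at the lower level, it asks for 0/6 where 11.2 accepts 1/6. It is stricter than 11.2 on fallback and looser at the top dose, so it cannot be a summary of 11.2. And 150 mg is carried forward without the six patients that 11.2 requires, whatever the label.

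**Conclusion.** The concern holds: the plan is wrong as written and should be corrected before the rules are applied. It contains two acceptance rules for its primary endpoint and no order of precedence. On the literal 2/6 trigger, the sections diverge in 15% to 32% of trials and the accepted level differs in 8.5% to 11.2%; on the two-or-more trigger the upper bounds are 39% to 41% and 14% to 28%. These figures rest on the three assumed sets of DLT rates and on treating a level that 6.2.1 leaves unnamed as not accepted. The textual conflict depends on neither assumption. Table 1.1 is correct. The missing DLT count in 5.4 is a lesser point.

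**What to change.** Keep 11.2 rules (1) to (4) as the single algorithm.

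- In 6.2.1, replace the sentences on de-escalation, the MTD and the top dose with a reference to 11.2, so that any candidate MTD, 150 mg included, needs six patients with at most one DLT.
- In 5.4, make the move to 75 mg conditional on two or more DLTs in the 100 mg cohort.
- In 11.2, state that rule (3) is subject to rule (4), including when the previous level is an untested 75 mg.
- Delete the expansion phase, or define it and count its patients in 11.3.
- Leave Table 1.1 as it is.

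The cost is a wording amendment. Compared with 6.2.1, it means up to three more patients at 150 mg, which rule (4) already foresees, and three fewer at a fallback level already at 1/6.
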